Study Title: Louisiana Community-Engagement Alliance (LA-CEAL)

1. Study aim, background, and design

In August 2020, Louisiana (LA) ranked first in the US for COVID-19 cases by population with a case rate of 2,960 per 100,000 and fifth in deaths by population with a death rate of 97 per 100,000.¹ Furthermore, there were disturbing demographic trends in LA with Blacks representing the highest percentage of cases (40.2%) and second highest percentage of deaths (48.7%).² At that time, vaccines for prevention of COVID-19 were in development.³ To reduce COVID-19-related morbidity and mortality, an approved vaccine needed to be disseminated with rapid uptake in the community. Mistrust of the health care system and experimentation create barriers to rapid and widespread acceptance of novel COVID-19 preventive and therapeutic interventions (including vaccines) among underrepresented groups.⁴ The objective of this study is to **rapidly implement and evaluate the HALT-COVID program designed to address barriers and increase knowledge about COVID-19, vaccines, and availability of trials that informs decision-making about willingness to participate (WTP) in COVID-19 prevention (e.g., vaccines) and therapeutic initiatives and trials in underrepresented Louisianians.**

To accomplish this objective, we will conduct a **randomized controlled trial** to test the effectiveness of HALT COVID educational outreach by HALT COVID Ambassadors. HALT COVID Ambassadors will receive training to answer common vaccine questions & address misconceptions; conduct motivational interviewing (which has shown promise for reducing vaccine hesitancy); implement basic behavioral economics and related strategies to remove barriers to vaccination; and assist with scheduling vaccine appointments. Participants will be identified via multiple recruitment strategies including:

- **Random sample drawn from FQHC EHR data downloads:** EHR data downloads of adult patients seen in the last year will be used to draw random samples of persons to be contacted by telephone.
- **In-clinic recruitment:** via LA-CEAL staff who will directly approach clinic patients to inform on study activities, gain consent and assess eligibility.
- **Snowball sampling techniques:** potential (i.e., persons who have been screened, regardless of final eligibility determination) and enrolled participants will have the opportunity to refer persons they feel may be interested in participating.
- **Referrals from partners (including FQHC, FBO, and pharmacy partners):** persons will be recruited via flyers that are posted at partner locations or distributed at community events, in addition to in-person recruitment and telephone-based recruitment by partner staff using member/patient lists or other referrals.
- **Ambassador identification and enrollment:** HALT-COVID Ambassadors will have opportunities to recruit persons using contacts made during fieldwork and community events.
- **Internet (digital displays & video) and radio advertisements** developed and disseminated by communications and public relations partner.

Eligibility will be based on the following criteria: vaccine hesitancy, age ≥ 18 , Black, able to understand and speak English, and willing to engage with the HALT COVID Ambassador via in-person or virtual sessions exploring their own questions and concerns about vaccines. A total of 100 individuals will be enrolled into the trial and randomized to intervention (engagement by the Ambassador over a 1-month period) or usual care (no extra engagement). Baseline, 1-month, and 2-month follow-up surveys will assess for change in vaccine hesitancy.

2. Subject Population

Using the following criteria, we will enroll up to 100 participants from patient populations of partner FQHCs:

Inclusion criteria: Vaccine hesitancy; age ≥ 18 years; Black; ability to understand and speak English; willingness to engage with the HALT COVID Ambassador via in-person or virtual sessions exploring their own questions and concerns about vaccines

Exclusion criteria: Unable or unwilling to give informed consent

Multiple strategies will be used to recruit participants including telephone calls to a random sample of adult patients served in the past year (identified in the EHR); in-clinic recruitment by LA-CEAL staff of clinic patients from partner FQHCs; snowball sampling methods, offering potential and enrolled participants the opportunity to refer others; referrals from FQHC, FBO pharmacy, and other partners using flyers, direct communication at partner locations and community events, and telephone-based recruitment to identify and recruit potential participants; Ambassador identification and enrollment during fieldwork and community events; and internet (digital displays and video) and radio advertisements.

Eligibility criteria will be confirmed prior to enrollment into the study.

3. Procedure

After obtaining verbal consent, study staff will verify participant contact information, collect alternate contact information for a friend or family member who is likely to be able to reach the participant in the event the study staff cannot, conduct a baseline questionnaire, and reveal the results of the randomization procedure conducted by the LA-CEAL Study and Data Coordinating Center staff. Participants will be randomly assigned to intervention (HALT COVID Ambassador engagement) or usual care. Participants randomized to the intervention will be engaged over a one-month period in discussions by the HALT COVID Ambassador; identified concerns or barriers around vaccination will be addressed, drawing upon the training and resources provided through the LA-CEAL program. We anticipate a total of 3-4 engagements over the month, each lasting 30 minutes to 1 hour. Discussions will take place in-person at a location mutually agreed upon by the participant and Ambassador, or virtually via telephone or web-based video platform (e.g., Zoom). Usual Care participants will not receive any additional outreach during this one-month period. After one month, all participants will be re-contacted via telephone by LA-CEAL staff to complete a month 1 follow-up survey. Following a one-month maintenance period (no intervention delivery), all participants will be re-contacted via telephone by LA-CEAL staff to complete a month 2, follow-up sustainability survey. Study staff will contact participants by text or phone to confirm and remind of all study and Ambassador visits.

4. Risks

The risk of physical, psychological, social, or legal harm associated with participation in all components of this study is minimal:

- Though not sensitive in nature and widely used in social science research, participants may feel uncomfortable responding to some of the survey questions; participants will be informed that they do not have to answer any question they do not want to answer and that they can stop participating at any time without penalty.
- Participants may find it inconvenient to take time to participate in the study. All study activities will be arranged at a time that is convenient for participants. The option to complete study activities via telephone or Zoom will also ease the burden of participation for participants.
- There is a small risk of unauthorized disclosure of participants' responses, which will be prevented by following a strict protocol for data handling and rigorous training of study staff:
 - All electronic study records will be stored with password protection. All paper study records will be locked in a secure study office. Data will be accessible only by study staff with approval from the PI.
 - The data will be retained without identifiers in a secure location for possible use in a future project, which will be consistent with the original research purpose.
 - Data may be shared with the NIH or other researchers upon request. Any data shared with the NIH or other researchers will not contain identifying information.
 - Identifiers will be stored in REDCap for the purposes of study management and follow-up. Study data will be stored separate from identifiers and a master key linking study data to identifiers will

be stored electronically in a separate REDCap database. Upon completion of all data collection and verification activities, records linking identifying information to study data will be destroyed.

5. Benefits

Individuals randomized to the intervention could benefit from engagement with the HALT COVID Ambassador which provides COVID-19 information and messages that may change their attitudes toward vaccines and remove barriers, thereby leading to vaccination and reduction in risk of severe COVID-19 infection. The knowledge to be gained may benefit society in general by providing evidence about the effectiveness of an approach for reducing vaccine hesitancy and increasing vaccine uptake.

6. Remuneration

Participants who complete the baseline and follow-up surveys will receive remuneration in the form of a \$25 gift card for each survey completed (up to \$75).

In addition, potential and enrolled participants will receive a \$10 gift card for reimbursement of time used to recruit others (per person ultimately enrolled, up to five persons per referring individual).

Participants who are randomly assigned to the intervention will also receive remuneration in the form of a \$15 gift card for each Ambassador session completed (up to \$60).

7. Costs

There will be no costs to the participant for participating in this research study.

8. Consent process and documentation

Participants will be identified via multiple recruitment strategies:

- **Random sample drawn from FQHC EHR data downloads:** FQHC staff will query EHR records to generate a list of potentially eligible patients based on age and status (seen in last year). Only name and contact information will be listed on data downloads provided to LA-CEAL staff. We are requesting a *waiver of HIPAA Authorization* and a *waiver of informed consent* for this step in the recruitment process. A random sample of FQHC patients will be drawn from lists and contacted via telephone by LA-CEAL study staff. A recruitment script will be used to introduce the study and a consent script that explains the study purpose, procedures, risks and protections, and benefits will be read to interested patients. Verbal consent will be obtained and eligibility will be assessed before administration of the baseline survey. We are requesting a *waiver of documentation of informed consent* for this study activity given the nature of the risk associated with participating in the study (minimal) and the fact that most or all study activities will be conducted via telephone or web-based video platform (e.g., Zoom).
- **In-clinic recruitment:** LA-CEAL staff will approach clinic patients in private clinic rooms to inform on study activities, gain consent and assess eligibility. A recruitment script will be used to introduce the study and a consent script that explains the study purpose, procedures, risks and protections, and benefits will be read to interested patients. Verbal consent will be obtained and eligibility will be assessed before administration of the baseline survey. We are requesting a *waiver of HIPAA Authorization* and *waiver of documentation of informed consent* for this study activity given the nature of the risk associated with participating in the study (minimal).
- **Snowball sampling techniques:** potential (i.e., persons who have been screened, regardless of final eligibility determination) and enrolled participants will have the opportunity to refer persons they feel may be interested in participating. Study flyers and contact information for study staff will be provided to potential and enrolled participants for passing on to other potential participants. Those individuals will contact LA-CEAL study staff through the study telephone number. A recruitment script will be used to introduce the study and a consent script that explains the study purpose, procedures, risks and protections, and benefits will be read to interested patients. Verbal consent will be obtained and eligibility will be assessed before administration of the baseline survey. We are requesting a *waiver of HIPAA Authorization* and a *waiver of documentation of informed consent* for this study activity given the

nature of the risk associated with participating in the study (minimal) and the fact that most or all study activities will be conducted via telephone or web-based video platform (e.g., Zoom).

- **Referrals from partners (including FQHC, FBO, and pharmacy partners):** persons will be recruited via flyers that are posted at partner locations or distributed at community events, in addition to in-person recruitment and telephone-based recruitment by partner staff using member/patient lists or other referrals. The IRB-approved recruitment script will be provided to partner staff for use in recruitment efforts. In addition, study flyers and contact information for study staff will be provided to partners for passing on to potential participants. Interested individuals will contact LA-CEAL study staff through the study telephone number. A recruitment script will be used to introduce the study and a consent script that explains the study purpose, procedures, risks and protections, and benefits will be read to interested patients. Verbal consent will be obtained and eligibility will be assessed before administration of the baseline survey. We are requesting a *waiver of HIPAA Authorization* and a *waiver of documentation of informed consent* for this study activity given the nature of the risk associated with participating in the study (minimal) and the fact that most or all study activities will be conducted via telephone or web-based video platform (e.g., Zoom).
- **Ambassador identification and enrollment:** HALT-COVID Ambassadors will have opportunities to refer persons using contacts made during fieldwork and community events. The IRB-approved recruitment script will be provided to Ambassadors for use in recruitment efforts. In addition, study flyers and contact information for study staff will be provided to Ambassadors for passing on to potential participants. Interested individuals will contact LA-CEAL study staff through the study telephone number or will give their contact information (name and phone number) to the Ambassador for contact by LA-CEAL study staff. A recruitment script will be used to introduce the study and a consent script that explains the study purpose, procedures, risks and protections, and benefits will be read to interested patients. Verbal consent will be obtained and eligibility will be assessed before administration of the baseline survey. We are requesting a *waiver of HIPAA Authorization* and a *waiver of documentation of informed consent* for this study activity given the nature of the risk associated with participating in the study (minimal) and the fact that most or all study activities will be conducted via telephone or web-based video platform (e.g., Zoom).
- **Internet (digital displays & video) and radio advertisements:** A communications and public relations firm will develop and disseminate internet (using both video and digital displays) and radio advertisements. Prospective participants will be directed to self-complete a virtual pre-screening/interest form. Those meeting initial inclusion criteria and providing contact information will be contacted by the LA-CEAL research team. A recruitment script will be used to introduce the study and a consent script that explains the study purpose, procedures, risks and protections, and benefits will be read to interested patients. Verbal consent will be obtained and eligibility will be assessed before administration of the baseline survey. We are requesting a *waiver of documentation of informed consent* for this study activity given the nature of the risk associated with participating in the study (minimal) and the fact that most or all study activities will be conducted via telephone or web-based video platform (e.g., Zoom).

9. References

1. Centers for Disease Control and Prevention. CDC COVID Data Tracker. <https://www.cdc.gov/covid-data-tracker/#cases>. Published 2020. Updated Aug 19 2020. Accessed Aug 19 2020.
2. Louisiana Department of Health. COVID-19. <https://ldh.la.gov/Coronavirus/>. Published 2020. Updated Aug 19 2020. Accessed Aug 19 2020.
3. World Health Organization. DRAFT landscape of COVID-19 candidate vaccines. World Web site. <https://www.who.int/publications/m/item/draft-landscape-of-covid-19-candidate-vaccines>. Published 2020. Accessed Aug 24 2020.

Statistical Analysis Plan

Baseline demographics will be summarized using means and standard deviations or proportions as appropriate. Between-group differences in the proportions of participants for each outcome will be tested using Pearson's chi-squared tests.

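### Does letting enrolled participants refer acquaintances, with no plan to record or report ties across arms, require a change to the plan?

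*Combined protocol and SAP*

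**What the plan says.** Section 2 lists snowball methods among six recruitment strategies, "offering potential and enrolled participants the opportunity to refer others". Section 8 gives the mechanism: "enrolled participants will have the opportunity to refer persons they feel may be interested in participating". Potential referrers are defined as "persons who have been screened, regardless of final eligibility determination", so a referrer need not be in the trial. Recruits are not signed up by the referrer: "Those individuals will contact LA-CEAL study staff through the study telephone number". Section 6 pays the referrer a $10 gift card, "per person ultimately enrolled, up to five persons per referring individual".

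Section 3 makes the individual the unit of allocation: "Participants will be randomly assigned to intervention (HALT COVID Ambassador engagement) or usual care". It has no rule for people who know each other, and the allocation ratio is not stated. Section 2 sets the total at up to 100.

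On data handling, Section 4 says: "The data will be retained without identifiers in a secure location for possible use in a future project". It adds that, once collection and verification are complete, "records linking identifying information to study data will be destroyed". The SAP has two sentences, one on baseline summaries and one on Pearson chi-squared tests for each outcome. Neither mentions referral ties.

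**The concern.** The intervention is conversation about vaccine concerns, which an acquaintance can pass on. If an intervention participant and a usual-care participant are linked by referral, some of the effect may reach the usual-care side and pull the difference toward zero. With 1:1 allocation (assumed), about half of the pairs in which both people enrol would be split across arms.

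Paying the $10 means staff must know who referred whom. However, the plan does not say that this information enters the de-identified data, and the identity links are later destroyed. A reader of a null result might then be unable to tell whether ties were too few to matter. The five-person cap does not settle this, because it limits paid referrals per person and not the number of ties across arms.

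**Working it through.** The documents give no power, effect size, outcome rates, allocation ratio, snowball share or spillover, so there is no stated figure to reproduce. What follows is illustration.

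**From the documents:** N = 100, individual randomisation, Pearson chi-squared test.

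**Assumed:** 1:1 allocation (50 per arm), two-sided 5%, 20% favourable outcome in usual care and 45% in intervention, no dropout.

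**Share of split pairs.** Given one member's arm, 50 of the other 99 places are in the opposite arm: 50/99 = 50.5%.

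**Dilution.** Let r be the share of all participants recruited by an enrolled participant. In simple pairs, 2r of participants belong to a pair and half the pairs split. The share e of usual-care participants exposed is then r if influence runs in both directions, or r/2 if it runs only from a treated referrer to a usual-care recruit. With t the fraction of the effect passed on:

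loss = 0.25 × e × t; usual-care rate = 0.20 + loss.

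Power is the exact power of the Pearson test at 50 per arm. With no leakage it is 77.2%. The ranges below run from e = r/2 to e = r.

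| r | t | Loss (points) | Power |
|---|---|---|---|
| 5% | 0.5 | 0.31 to 0.63 | 76.0% to 74.7% |
| 10% | 0.5 | 0.63 to 1.25 | 74.7% to 72.2% |
| 20% | 0.5 | 1.25 to 2.5 | 72.2% to 66.9% |
| 20% | 1 | 2.5 to 5.0 | 66.9% to 55.8% |

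The standard error of the difference is √(0.45×0.55/50 + 0.20×0.80/50) = 9.0 points, so even the 5-point loss is smaller than one standard error.

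The answer depends on the inputs. In a second illustration (20% versus 46%, 80% power without leakage), referral trees with at most five recruits per person were simulated. If half of all participants were recruited by another participant, about 41% of usual care had a direct tie to an intervention participant. With 42% tied, power is 58% at t = 0.5 and 34% at t = 1. Such a snowball share is possible in principle, but nothing in the documents points to it: the route is one of six, and recruits must telephone the staff themselves.

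**False positives.** Arms are allocated without regard to ties, so correlated outcomes within pairs do not bias the test. A simulation with 30% in both arms, r = 20% and within-pair correlation 0.5 rejected in 5.1% of 20,000 trials.

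**What a tie count could show.** Let x be the number of usual-care participants who are tied to an intervention participant and have the favourable outcome. If leakage acts only toward that outcome, x/50 is the most it can have raised the usual-care proportion. Take a null result of 20/50 versus 14/50 (p = 0.21). With x = 1 the extreme case is 20 versus 13 (p = 0.14). With x = 4 it is 20 versus 10 (p = 0.03). So the count can inform how a null is read, but only under that proviso. All participants are vaccine hesitant at entry, so a usual-care acquaintance could also hold back an intervention participant. That dilutes the difference too, and x does not capture it. When such reverse influence (0.5) was added to simulated referral trees with r of 5% to 20%, total dilution exceeded the limit in about 15% to 21% of trials.

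**Does the destruction clause lose the ties?** It covers records that join identity to study data. A coded referrer number held in the dataset is not such a record, so the clause does not require its removal. The document lists no data fields at all, so silence about this one says little.

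**The case for a change.** The strongest case for a change is that it is cheap and time-limited. The $10 payment already requires the referral link. Two coded variables and one SAP sentence would preserve it, with no effect on recruitment, sample size or the main test. If the link lives only in payment records, it can no longer be joined to arm or outcome once the key is destroyed. If ties prove few, a count would largely remove favourable leakage along them as an explanation for a null result.

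Much of this stands. The plan makes no commitment to keep or report ties, and keeping a code is easy. Three things limit its weight. First, the count does not bound total dilution: it misses reverse influence, tied participants with missing outcomes, and contact never recorded as a referral, such as between people recruited from the same Ambassador's contacts or the same partner site. Second, it has a confidentiality cost. Section 4 allows sharing of data without identifiers, and in a sample of 100 a referrer code or a published cell of one could reveal an acquaintance's answers to the person who referred them. That risk is greatest when ties are few, which is also when the count is most informative. Third, the trial's estimate and test would be the same with or without it.

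**Conclusion.** No change to the plan is needed. The facts are as described: paid referral by participants, individual randomisation, and no statement that ties are kept or reported. However, this is missing detail that a study team can fill sensibly, and following the plan as written produces no wrong analysis. Any dilution would usually make the comparison conservative, although two tied intervention participants could reinforce each other and act the other way. Allowing referrals is a fair trade for reaching a hard-to-recruit population.

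The size cannot be fixed from the documents. With 5% to 20% of participants recruited by enrolled participants and half the effect passed on, the loss is 0.3 to 2.5 points and power falls from 77% to between 76% and 67%. Full spillover at 20% gives a loss of up to 5 points and 56% power. These figures rest on assumed rates, 1:1 allocation and simple pairs. The upper values also credit full influence from a later-enrolled recruit back to the referrer, which is generous for the referrer's month-1 survey.

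A team that wishes to can keep recruitment route and a coded referrer number in the restricted analysis file, leave them out of shared data, and report the number of cross-arm ties with small cells suppressed. That is a reporting preference, and its absence is not a flaw.

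### The SAP compares the arms only by chi-squared tests: with at most 100 participants it should also report each risk difference with a 95% confidence interval, adjusted for baseline hesitancy only if that is graded

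*Combined protocol and SAP*

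**What the plan says.** The Statistical Analysis Plan has two sentences. On baseline data: "Baseline demographics will be summarized using means and standard deviations or proportions as appropriate". On the comparison of arms: "Between-group differences in the proportions of participants for each outcome will be tested using" Pearson's chi-squared tests. Neither document part mentions a risk difference or ratio to be reported, a confidence interval, a regression model or a covariate.

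Four other statements bear on this:

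- Section 1 (Study aim, background, and design), on size: "A total of 100 individuals will be enrolled into the trial and randomized to intervention". Section 2 gives the same number as an upper limit.
- Section 1, on measurement: "Baseline, 1-month, and 2-month follow-up surveys will assess for change in vaccine hesitancy".
- Section 1, on entry: "Eligibility will be based on the following criteria: vaccine hesitancy".
- Section 3 (Procedure), on the order of events for staff: "conduct a baseline questionnaire, and reveal the results of the randomization procedure".

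Section 5 (Benefits) gives the purpose: "providing evidence about the effectiveness of an approach for reducing vaccine hesitancy and increasing vaccine uptake".

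**The concern.** A chi-squared test returns a p-value. It does not say how large the difference between arms is or how precisely it is known. In a trial this small, a non-significant result is a likely outcome even if the Ambassador programme has a useful effect. The p-value alone cannot separate no effect from too little information, so the evidence on effectiveness that section 5 promises would be missing from the planned output.

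The second, lesser part concerns baseline hesitancy. It is surveyed before anyone learns the allocation, so a graded value would be a legitimate covariate at no extra data-collection cost. The SAP does not name it. If it is graded and predicts follow-up hesitancy, some precision is given up.

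**Working it through.** **Inputs.** From the documents: 100 participants (section 1), and chi-squared tests of proportions (SAP). Not in the documents, so assumed: 1:1 allocation, two-sided 5% level, control proportions of 5% to 50%, dropout of 0% or 20%, and an effect of 0.5 SD on an underlying normal hesitancy scale. The total of 100 comes with no derivation, so there is no planned power figure to reproduce.

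**Step 1: width of the interval.** With control proportion p0, the intervention proportion is p1 = Φ(Φ⁻¹(p0) + 0.5). The half-width is 1.96 × √{[p0(1 − p0) + p1(1 − p1)]/n}. For p0 = 0.20, p1 = 0.366 and n = 50: 1.96 × √[(0.160 + 0.232)/50] = 17.4 points.

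| Control | Intervention | Half-width, 50 per arm | Half-width, 40 per arm |
|---|---|---|---|
| 5% | 12.6% | 11.0 | 12.3 |
| 10% | 21.7% | 14.1 | 15.8 |
| 20% | 36.6% | 17.4 | 19.4 |
| 35% | 54.6% | 19.1 | 21.4 |
| 50% | 69.1% | 18.9 | 21.1 |

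**Step 2: what a p-value would hide.** Take 15/50 against 20/50. Chi-squared = 100 × (15×30 − 20×35)²/(50×50×35×65) = 1.10, so p = 0.295. The Wilson limits are 19.10% to 43.75% and 27.61% to 53.82%. The Newcombe interval for the 10-point difference is:

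- lower: 10 − √[(40 − 27.61)² + (43.75 − 30)²] = −8.5
- upper: 10 + √[(53.82 − 40)² + (30 − 19.10)²] = +27.6

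With 15/50 in both arms, p = 1.00 and the interval is −17.5 to +17.5.

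**Step 3: how likely a non-significant result is.** In simulation (8,000 trials per setting, 50 per arm, control proportions 20%, 35% and 50%), the chi-squared test has power of about 46% to 53% for the 0.5 SD effect. About half of such trials would be non-significant.

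**Step 4: what adjustment could add if hesitancy is graded.** Here r is the within-trial correlation of baseline with follow-up hesitancy on the underlying scale. The comparison is a logistic-standardised risk difference against the unadjusted one, both with unpooled standard errors, at the same three control proportions.

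| r | Power, unadjusted (%) | Power, adjusted (%) | Half-width, adjusted (points) |
|---|---|---|---|
| 0 | 47.2 / 52.7 / 50.6 | 46.4 / 52.3 / 50.9 | no gain |
| 0.3 | 47.4 / 52.6 / 51.4 | 48.9 / 54.1 / 53.6 | 16.9 / 18.6 / 18.3 |
| 0.5 | 46.8 / 53.5 / 51.3 | 52.7 / 59.1 / 58.0 | 16.0 / 17.6 / 17.3 |
| 0.7 | 47.2 / 53.2 / 50.4 | 60.7 / 67.7 / 66.1 | 14.5 / 15.8 / 15.6 |

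Repeat runs gave up to about 4 points of power at r = 0.3 and 11 to 18 at r = 0.7, so the gains are good to a few points only.

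Entry on hesitancy probably narrows the range of baseline values. If the most hesitant 40% are enrolled (an assumption), correlations of 0.3, 0.5 and 0.7 fall to 0.17, 0.31 and 0.48. The power gains are then 0 to 0.6, 1.2 to 1.7 and 3.3 to 6.4 points. If baseline hesitancy is yes/no, everyone has the same value and the gain is exactly zero.

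**Step 5: where adjustment breaks down.** With 50 per arm and an outcome at 5% in both arms, the logistic model had no finite fit in about 14% of simulated trials. At 3% it failed in 35% to 38%. Simulated null rejection for the adjusted analysis was 5.4% to 6.1%, against 5.1% to 6.1% for the chi-squared test.

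**The case against.** The strongest reply has four parts.

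- **The interval loses no information.** The SAP speaks of differences in proportions and does not say that only p-values will be reported. If arm counts are published, any reader can compute the unadjusted interval. This is true and limits the seriousness. But the sentence plans a test, not an estimate, and a plan for an effectiveness trial should not leave the estimate to its readers.
- **The covariate part rests on a measure the documents do not show.** The instrument is not defined, hesitancy is an entry criterion, and the only planned comparison is of proportions. Surveys that assess change are compatible with a graded scale but do not establish one. Baseline hesitancy might also enter through an outcome's definition, such as being less hesitant than at entry. This stands, so adjustment can only be conditional.
- **Adjustment may gain little, or fail.** Selection on hesitancy shrinks the gain, and vaccine uptake over two months could be rare enough to break a logistic model. This stands too, so a fallback is needed and the chi-squared test should keep its place.
- **The 17 to 19 point figure is not universal.** It holds for control proportions of 20% to 50%. Rarer outcomes give narrower intervals, as the first table shows.

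A reader might infer that the unadjusted test is biased or wrong. The documents do not support that: allocation is random, and the test is valid without covariates.

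**Conclusion.** The point holds as an inexpensive improvement that should be made, not as an error. The missing estimate and interval come first, and that part does not depend on how hesitancy is measured, although the width depends on the outcome proportions. It is about ±17 to 19 points at control proportions of 20% to 50% and ±11 to 14 at 5% to 10%, under the assumed 1:1 allocation, 0.5 SD effect and no dropout. A 20% loss widens the first range to about ±19 to 21.

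The unused baseline measure is secondary and conditional. Within-trial correlation of 0 gives no gain, 0.3 gives about 2 to 4 points of power or less, and 0.5 gives about 6 to 7. The gains are smaller under range restriction and zero for a yes/no measure. A reader might infer that the trial forfeits substantial power by not adjusting. That would need a graded scale and a correlation near 0.7 among people all chosen for being hesitant, and the documents give no basis for either.

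**What to change.** Add to the SAP:

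> For each binary outcome, the between-arm risk difference (participants as randomised) is reported with a Newcombe 95% CI beside the Pearson chi-squared test. If the baseline survey grades hesitancy, a risk difference adjusted for baseline hesitancy level (logistic model standardised over the baseline distribution, with a robust or influence-function standard error) is also reported. If the model does not converge or events are too few, by a threshold set in advance, the unadjusted risk difference and interval stand.

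State before outcome data are seen whether the graded branch applies. The outcomes and the hesitancy instrument must be defined first, which is a separate point.

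The cost is a few sentences and a little analysis time. No visit, survey question or participant is added. The downside is confined to the adjusted result: it depends slightly on a model, and its interval may be slightly too narrow at this size (simulated null rejection of about 6% against a nominal 5%).
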